11.1 Demographics

Individual patient demographics (age, gender and race) and body measurement data (height, weight, body mass index and head circumference) at study start will be listed.

Age will be counted in months. Height will be measured in centimetres and weight in kilograms. BMI (kg/m²) will be calculated from the height and weight.

These demographic characteristics and body measurements will be summarized for the total safety analysis set and the pivotal sub group.

11.2 Baseline characteristics

Other baseline measurements that will be listed include DQ, AEQ and genotype. The listing will include the NH study as well.

11.3 Medical history

Medical and surgical history will be coded using the Medical Dictionary for Regulatory Activities (MedDRA) (version 16.1 or higher). All medical history events will be listed by system organ class (SOC) and preferred term. Surgical history will be presented in a separate listing.

12 Prior and concomitant medication

All prior and concomitant medication will be coded using the latest version of World Health Organization drug dictionary (WHO Drug) version June 1 2013.

Prior medications are defined as those for which the end date is prior to Day 1. Concomitant medications are defined as those which are indicated as ‘Ongoing’ on Day 1, those which start on or after Day 1 and those which start prior to Day 1 and have an end date on or after Day 1.

If medication dates are incomplete and it is not clear whether the medication was concomitant, it will be assumed to be concomitant.

The number and percentage of patients who took any concomitant medications will be presented by medication class and standardized medication names sorted alphabetically.

All prior and concomitant medications will be listed by reported name, medication class, standardized medication name, indication, dose, dose unit, frequency, route of administration, start date and end date or ‘ongoing’ flag and duration of use. Concomitant medications will be flagged.

13 Treatment compliance

There will be no measurement of, or analysis of, treatment compliance, nor does it affect population assignment (patients must be exposed to IMP to qualify for the analysis sets).

14 Efficacy analyses

14.1 The DQ endpoint

One of the key secondary objectives is to assess the effect of SOBI003 on neurocognition, as compared to untreated MPS IIIA patients from a NH control. The key endpoint related to this

objective is the change from baseline in DQ of neurocognitive development at 104 weeks of treatment, and will be estimated by a model based contrast.

To address the efficacy objective, a repeated measure analysis will be utilized where DQ is the response variable and time, baseline age, time*baseline age and treatment*time are fixed effects and the dependency between observations within the same patient is represented by an unstructured variance-covariance matrix.

The time window is two weeks, i.e., if the assessment is more than two weeks too early or more than two weeks too late, then the DQ is set to missing for that assessment.

In the NH study, a simple linear regression model was used, i.e. with DQ as the response variable and the age of the child as dependent variable (Shapiro et al 2016). As the aim in this clinical development program is to demonstrate that treatment with SOBI003 is efficacious and the effect of treatment is dependent on the time the patient has been treated, this model needs to be adopted so that time and baseline age are factors rather than the actual age of the child (which is the sum of the baseline age and the time in study). The results from the NH study suggest that the decline in DQ is not linear across all ages, and an interaction term time*baseline age is planned to be included in the model to allow for such a non-linearity. Also an unstructured variance-covariance matrix is planned to be used to account for the dependency between observations within the same patient. As a further justification for the model, it should be noted that time, baseline age and time*baseline age are all significant factors in the NH study.

To represent the treatment effect without constraint to a specific relation across visits, a term treatment*time is planned to be included in the model. This effect is used to judge the treatment effect. The null hypothesis of no treatment effect will be tested with a significance test for the treatment*time-effect in the second step of the multiple testing procedure (see Section 14.3). The difference between 104 weeks and baseline will be used as the contrast of interest for the test.

All missing values will be imputed. For a patients who stops treatment, let tp denote the turning point, i.e., the time point when the patient stops treatment. The patient's assessments as well as the time points for prediction are classified as being on either side of the turning point or at the turning point: prior to tp , at tp , or after tp . For patients who does not stop treatment, let $tp = \infty$, i.e., every time point is considered as prior to the tp . Let v denote a missing value to be imputed for a patient. The imputations will be based on two categories of predictions.

1). If the patient has two or more observations on the same side of tp as v (including a possible observation at tp), then v is considered as *exclusively patient-predictable* (p_1), i.e., it can be predicted by simple linear regression based only on the patient's data (intra-or extrapolation). On the other hand, if only one or zero observations exists on the same side of tp (from the particular patient) as v (including a possible observation at tp), then it is considered as *non-predictable exclusively* from the patient's data.

2) The other type of prediction (p_2), will be calculated by the use of a population derived slope, estimated based on the repeated measures model in Section 14.1 (without imputations), and a patient observation. There will be two cases: If the patient has one or more observations on the same side of tp as v (including a possible observation at tp), then the nearest observation will be used together with a slope, which is based on the population (treated or untreated) of the same

status as the side of tp where the prediction time point is situated, as well as the interval relative the visits which contain the prediction time point. The other case is when there is no observation on the same side of tp as v (and no observation at tp). In this case, a prediction at tp will first be calculated, based on the same method as described above (under 2) but on the other side of tp , i.e., the nearest observation relative tp on the other side of tp will be used together with a slope based on the population (treated or untreated) of the same status as the side of tp where this nearest observation time point is situated, as well as the interval relative the visits which contain the tp . This prediction at the tp is in then used to predict v as described under the first case (under 2).

For each missing value v , the following algorithm is used to impute v by i .

If p_1 does not exist, then p_2 is used, i.e., $i = p_2$.

Otherwise, a weighted average will be used for the imputation: $i = w_1 p_1 + w_2 p_2$, where $w_1 = \exp(-\lambda \ln(2)/3)$ and $w_2 = 1 - \exp(-\lambda \ln(2)/3)$ and λ is the distance in months between the time point for prediction and the nearest available non-missing patient assessment time point. The exponential function is motivated by an exponential decrease of relevance of individual patient data relative to population data with increasing time, and the coefficient $\ln(2)/3$ is chosen such that population data reach the same weight as individual patient data after 75 % of the distance between two visits, i.e., three months. When individual patient data is available near a missed visit, the patient data weight is near 100 %, and when the distance is near one year on the other hand, the individual patient data weight has decreased to nearly 6 %.

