5.2 Analyses and reporting

All final, planned, analyses identified in the protocol and in this SAP will be performed only after the last patient has completed the study.

Any post-hoc analyses included in the CSR, which were not identified in this SAP, will be clearly identified as such in the relevant section of the CSR.

For each patient in the study, all the associated safety and efficacy data in the SOBI003-001 study will be pooled and presented together with the SOBI003-002 study. Thus the SOBI003-001 study and the SOBI003-002 study are considered as a single, unified entity.

6 Estimands

There will be a de facto estimand in the study, which is the primary estimand for the evaluation of efficacy. The estimand is the change in

- cognitive decline in all the patients from the population captured by the inclusion and exclusion criteria (see Section 4.2.1 and Section 4.2.2) and the part of the NH population with a rapid progressive disease having a baseline age of 12 to 72 months, irrespectively of other medications used and adherence to treatment, and estimated by a repeated measures model of the change from baseline in DQ as described in Section 14.1.

- decline in HS levels in CSF in all the patients from the population captured by the inclusion and exclusion criteria (see Section 4.2.1 and Section 4.2.2) irrespectively of other medications used and adherence to treatment, and estimated by a repeated measures model of the change from baseline in HS as described in Section 14.1.

To address foreseeable inter-current events, such as drop-outs, all missing values will be imputed (see Section 14.1) in accordance with the treatment policy principle. A sensitivity analysis will be performed where no imputations are performed, but all values are used: If a patient has a missing value in any assessment, then the same patient's non-missing scores will be used in the repeated measures model. The repeated measures model (see Section 14.1) handles missing values based on the missing at random (MAR) assumption. One further sensitivity analysis for DQ will address this assumption based on zero imputations (see Section 14.1.1), the rationale being that the patients not assessed are those expected to have a severe DQ decline. Other sensitivity analyses for this purpose will be tipping point analyses, see Section 14.1.1.

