9.1 Handling of missing data

All missing DQ values and HS in CSF values will be imputed. The procedure is fully described in Section 14.1. A sensitivity analysis will be performed where no imputations are performed, but all values are used: If a patient has a missing DQ score in any assessment, then the same patient's non-missing scores will be used in the repeated measures model. The repeated measures model (see Section 14.1) handles missing values based on the MAR assumption. One further sensitivity analysis will address this assumption based on zero imputations (see Section 14.1.1), the rationale being that the patients not assessed are those expected to have a severe DQ decline. Another sensitivity analysis for this purpose will be a tipping point analysis, see Section 14.1.1.

If an adverse event (AE) has a completely missing onset date, then the AE will be considered a TEAE, unless the (partial) stop date indicates differently. A medication with a completely missing start date is considered a prior medication. A medication with a completely missing stop date is considered a concomitant medication. If an AE or a medication has a partial missing start or stop date, the following rules will be used to impute the date. The imputed date will be used to determine whether it is a TEAE for adverse event, or a prior or concomitant medication.

Table 1 Partial date derivation

Partial Missing Start or Stop Date	Derived Start Date	Derived Stop Date
Missing month and day, and the year is present	January 1 st of that year or first dose date if the year is the same as the year of first dose date	December 31 st of that year

Partial Missing Start or Stop Date	Derived Start Date	Derived Stop Date
Missing day, but year and month are present	First day of that month or first dose date if the year and month are the same as the year and month of first dose date	Last day of that month
Missing month, but year and day are present	Missing month derived as January or same as first dose month if the year is the same as the year of first dose	Missing month derived as December

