9.3 Derived and computed variables

Scores (AEq and DQ) for neurocognitive development

Neurocognition is assessed at Weeks 52 and 104, and during Early Termination, by use of the neurocognition domain of the BSID-III and/or the KABC-II Nonverbal Index (NVI).

The selection of neurocognitive assessment method is done at the baseline assessment of the FIH study ([SOBI003-001](#)) based on the algorithm presented in **Error! Reference source not found.** The neurocognitive test(s) applied in the FIH study should also be used in the extension study.

Table 2 Selection of neurocognitive assessment method

Chronological age at the assessment time point	Development age-equivalence as established by VABS-II adaptive behavior composite	Neurocognitive test to apply
<42 months	Any age-equivalence	BSID-III
≥42 months	<36 months	BSID-III
≥42 months	36 to 42 months	BSID-III + KABC-II*
≥42 months	>42 months	KABC-II

* The BSID-III should be administered first, and there should be at least 2 days until the KABC-II assessment in order to reduce KABC-II outcome bias of patient tiredness.

The neurocognitive developmental age (months) is derived on the basis of the BSID-III cognitive total raw score and BSID-III age-normative data.

The neurocognitive developmental age (months) is derived from the mean AEq scores on the NVI of the KABC-II, where an AEq scores is the average score for a particular age.

Development Quotient

DQ is calculated as the AEq for cognitive development divided by the chronological age of the child multiplied with 100, i.e.

$$DQ = 100 * AEq / Age$$

For patients completing an assessment of both BSID-III and KABC-II, the BSID-III score will be used as a basis for calculating the DQ of neurocognitive development at baseline. A calibration of overlapping AEq scores between BDID-III and KABC-II will be done to assess if a patient outgrows the BSID-III test during the duration of the study. If confirmed, assessments of KABC-II will form the basis for calculating DQ of neurocognitive development for remaining study assessments.

10 Patient disposition

The following patient disposition details will be summarized and will include the number and percentage of patients:

- Included in the each study population (Safety analysis set, efficacy analysis set, immunogenicity analysis set, PK analysis set and PD analysis set)
- Completed the study
- Prematurely withdrew (including a breakdown of the primary reasons for withdrawal)

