14.1.1 Sensitivity analyses of the DQ endpoint

In order to assess the sensitivity of the model, the DQ model described in Section 14.1 will

- Only use non-missing values, i.e., no imputations will be performed
- Be extended with a triple interaction factor time*treatment*baseline age
- Use DQ = 0 for missing DQ values

An additional sensitivity analysis will be a tipping point analysis: All combinations of DQ values (n_{UN}, n_T) where $n_{UN}, n_T \in \{0,1,2,\dots,100\}$ are substituted for missings in the untreated arm and the treated arm respectively. P-values will be calculated for each combination.

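### SAP 14.1 sets a DQ score taken more than two weeks off schedule to missing and imputes over it, and the DQ = 0 sensitivity analysis then scores that tested child 0

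*SAP*

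**What the plan says.** SAP 14.1 applies a two-week window to each DQ assessment: "if the assessment is more than two weeks too early or more than two weeks too late, then the DQ is set to missing". The same section imputes all missing values from two predictions. The first (p1) is a straight line through the child's own observations. For the second (p2), "then the nearest observation will be used together with a slope, which is based on the population". The weight on p1 falls with the distance in months to "the nearest available non-missing patient assessment time point". The accompanying explanation adds: "When individual patient data is available near a missed visit, the patient data weight is near 100" per cent.

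SAP 14.1.1 lists the sensitivity analyses. One uses only non-missing values. Another reads "Use DQ = 0 for missing DQ values". SAP 9.1 introduces the latter with "One further sensitivity analysis will address this assumption based on zero imputations", and Sections 6 and 9.1 both give the reason: "the rationale being that the patients not assessed are those expected to have a severe DQ decline".

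Protocol 9.4.4.1 contains the same imputation algorithm but no DQ window, so it does not settle how an off-window score is treated.

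**The concern.** A child tested on day 15 after the due date has a measured outcome. The window rule turns it into a missing value, and the word non-missing in the weight formula then bars it from being the nearest observation. The plan replaces a measurement that is slightly mistimed with a prediction resting almost wholly on other children. The remark about patient data near a missed visit suggests that such data were expected to count. Outside Early Termination, the extension schedules DQ only at Weeks 52 and 104, so it is hard to see what else could lie near a missed visit. Two programmers could therefore build different datasets for the key cognitive endpoint.

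The DQ = 0 analysis has a second problem. It is justified by the expectation that children who could not be assessed had declined severely. A child tested outside the window was assessed, yet receives the worst possible score.

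The comparison is planned with 9 treated children against 14 controls, so a single child matters.

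**Working it through.** **Inputs.** SAP 7.1: control decline 30.4 (SD 12.1) over 104 weeks, baseline DQ 58.9, n = 14; assumed treated decline 9.8 (SD 13.0), n = 9; target difference 30.4 − 9.8 = 20.6. SAP 14.1: weight on p1 is w1 = exp(−λ·ln2/3) = 2^(−λ/3), with λ in months.

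**Step 1: the plan's own figure.** At 3 months w1 = 0.50. At 12 months w1 = 2^(−4) = 0.0625, which matches the stated weight of nearly 6%. At 15 days (0.493 months) w1 = 0.892; at 21 days (0.690 months) w1 = 0.853.

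**Step 2: timing error that deletion avoids.**
- Control decline: 30.4/104 × 15/7 = 0.63 at 15 days; × 3 weeks = 0.88.
- Treated decline: 9.8/104 × 15/7 = 0.20; × 3 weeks = 0.28.

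**Step 3: error if the Week 104 score is deleted.** Take a child still on treatment whose only other DQ scores are baseline and Week 52. Let D1 and D2 be the changes in years 1 and 2. Then p1 = Week 52 + D1, p2 = Week 52 + population change, and the imputed value is Week 52 + 0.0625·D1 + 0.9375·(population change). The documents give no yearly figures, so assume equal yearly means and variances, correlation r between D1 and D2, and a known population slope. With s = SD/√(2(1+r)), the error SD is s·√(1 + 0.0625² − 2·0.0625·r):
- SD 13.0: 9.21 (r = 0), 7.28 (r = 0.5), 6.09 (r = 1).
- SD 12.1: 8.57, 6.78, 5.67.

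**Step 4: error if the score is kept at its actual date.** Also assume linear change through year 2 and shortly after, and no test-retest error. For a test at Week 107, the line through Weeks 0, 52 and 107 evaluated at Week 104 weights the three scores −0.139, 0.324 and 0.814. Combining with p2 at w1 = 0.853 leaves an error of 0.118·D1 − 0.110·D2 about the mean. For a test 15 days late the error is 0.131·D1 − 0.126·D2.
- 21 days late, SD 13.0: 1.48, 0.86, 0.06 for r = 0, 0.5, 1; SD 12.1: 1.38, 0.80, 0.05.
- 15 days late, SD 13.0: 1.67, 0.97, 0.03; SD 12.1: 1.56, 0.90, 0.03.

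**Step 5: effect on the treated mean, one SD, one child.** Deleted: 5.67/9 = 0.63 to 9.21/9 = 1.02. Kept: at most 1.67/9 = 0.19. As a share of the target, 1.02/20.6 = 5%.

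**Illustration (invented child).** DQ is 58.9 at baseline, 54.0 at Week 52 and 40 when tested three weeks late; the population slope is −4.9 a year. The Week 104 value becomes 41.7 if the score is kept, 49.1 if it is deleted, and 0 in the DQ = 0 analysis.

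**Step 6: DQ = 0 analysis.** If the treated baseline equals 58.9, the expected Week 104 score is 58.9 − 9.8 = 49.1. Scoring one of nine children 0 instead moves the treated mean by 49.1/9 = 5.5 points against SOBI003, and the difference falls from 20.6 to 15.1.

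**The case against.** Missing can be read the same way throughout. On that reading the rule is determinate and deliberate: the score is out, and what remains is disagreement with a prespecified window. This is largely right about the literal text. It does not explain the remark about data near a missed visit, and it does not make deletion a good trade against a timing error below one point.

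Frequency is low. Infusions at Weeks 52 and 104 have a one-day window either side (Protocol 7.5.1.5 and 7.5.1.6), and DQ is tested within the following days. A deviation above two weeks should be exceptional in children on treatment. This stands. The likeliest cases are children who stop treatment and continue visits without infusions (Protocol 7.3.3.1).

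The 5.5 points arise only in a deliberately extreme sensitivity analysis. The tipping-point grid also shows the result near the observed score, provided that score is the only missing value in its arm. Both statements are correct and limit the priority.

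Keeping off-window scores at 85 to 89% own-line weight might seem to empty the window of meaning. It would still separate scores that enter the model directly from those that only inform a prediction, and the plan's own formula reduces the own-line weight with distance.

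A reader might extend the point to Early Termination tests, since "Neurocognition is assessed at Weeks 52 and 104, and during Early Termination". The documents do not support that. Those tests have no due date, so they cannot be too early or too late. SAP 14.1 already classes assessments as before, at or after the time of stopping and admits them as observations.

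**Conclusion.** The point holds, at minor priority. Taken literally, the SAP discards a measured DQ that is only slightly mistimed, and one sensitivity analysis scores that tested child 0 against its own rationale.

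In the main analysis, deletion replaces a timing error of 0.2 to 0.9 points with an imputation error SD of about 5.7 to 9.2, against at most 1.7 if the score is kept. One SD is about 0.6 to 1.0 point on the treated mean per affected child, at most about 5% of the target. These figures rest on equal yearly means and variances, yearly-change correlation between 0 and 1, linear change and no test-retest error. They describe a child with baseline and Week 52 on the same side of the stopping time as Week 104. For a child who has stopped treatment, different observations enter the prediction, and the size was not calculated.

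A reader might infer that one late test could overturn the cognitive conclusion. It could not do so through the DQ = 0 rule, because that analysis lies outside the hierarchical test in SAP 14.3. A reader might also infer a bias from the natural history controls. Their visit dates are not in the documents, so whether any fell outside the window is unknown. The documents give no count of off-window scores in either group.

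**What to change.** 1. In SAP 14.1, state that a DQ outside the two-week window stays a dated observation in the existing imputation (p1, p2 and λ) when the nominal visit is predicted, in both groups. The visit-based repeated measures model is unchanged.
2. In SAP 14.1.1, limit DQ = 0 to children with no DQ assessment for that visit.
3. Optionally, report literal deletion as a sensitivity analysis.

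The cost is two sentences, plus one extra run if the third item is used. The drawback is slight smoothing of the retained score, with an error SD of up to 1.7 points under the assumptions above. The wording should be settled before database lock. In an open-label study, deciding it later would mean choosing with knowledge of whose score is affected.
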